6 STATISTICAL METHODOLOGY FOR EFFICACY

6.1 *Planned analyses and definitions*

Protocol-specified analyses are foreseen at the time of the futility evaluation (approximately 40 patients in Arm A), final PFS analysis (main endpoint, approximately 210 progression or death events) and follow-up evaluation of OS at 24 months after the inclusion of the last patient or 80% of death events (approximately 200 death events), whichever occurs first. Accrual will be on-hold while data for the futility analysis is being assessed, when 40 patients in Arm A fully evaluable for response have been accrued.

6.1.1 *Early futility analyses*

An early futility analysis will be performed when information from the first 40 patients in Arm A are evaluable for response. A response rate (IMWG criteria) of at least 30% (12 or more responses by IRC review) will be taken as threshold for continuation of the study. A minimum response rate of 30% has been considered as clinically significant in this setting. This result will ensure that the lower limit of the exact binomial 95% Confidence Interval for the response rate will be greater than 15% (95% CI in case of 12 responses would be 16.6% - 46.5%).

However, the efficacy and safety information from all randomized patients in both arms at that time will be used by the IDMC to provide the sponsor with a recommendation for the further study conduct. No claim for superiority in efficacy will be formulated in this interim analysis and no alpha-spending for the analysis of PFS is foreseen.

6.1.2 *Final analyses*

Primary endpoint.

Efficacy will be assessed by comparing the PFS in each treatment arm.

Progression-free survival (PFS) is defined as the time from the date of randomization to the date of documented progressive disease (PD) by IMWG criteria or death (regardless of the cause of death). If the patient receives further antitumor therapy before PD, PFS will be censored on the date of the last disease assessment prior to the administration of this antitumor therapy. If the patient is lost to follow-up for the assessment of progression, or has more than one missing follow-up between the date of last tumor assessment and the date of progression, death or further antitumor therapy, the PFS will be censored at the date of last valid tumor assessment before the missing evaluations.

An external review committee blinded to treatment arm will assign the objective response and a progression or censoring date for each patient based on laboratory data, radiologic and bone marrow assessments when required and evaluation of all relevant clinical information; then, this information will be merged with the date of death from the death report forms and with further antitumor therapy data for the calculation of PFS. Patients with missing IRC evaluations will have their PFS censored at randomization date.

The primary study analysis will be based on externally assessed PFS data in the “All Randomized Patients” population, defined as all patients randomized to either treatment arm.

By design, disease response will be assessed every four weeks symmetrically across treatment arms irrespectively of treatment delays or omissions. Disease assessments (e.g., serum or urine M-spike, sFLC) and evaluation of extent of disease will be done within two weeks before randomization and every four weeks thereafter in the absence of PD while on treatment. If disease progression has not occurred at treatment termination, then disease assessments should continue every four weeks until evidence of disease progression or other antitumor therapy, whichever occurs first, and then will be followed every three months for survival until death, or until the date of study termination, whichever occurs first.

Study termination date is defined as the date in which 80% of death events occurred, 24 months after the accrual of the last randomized patient, or IDMC recommendation (whichever occurs first).

PFS and objective tumor response will be assessed according to IMWG criteria. Centralized laboratory reports and copies of computed tomography scans (CT-scans), magnetic resonance imaging (MRI) (in case of soft tissue plasmacytoma) and any other documented means to evaluate tumor response or progression should be available for IRC review.

For patients within the “All Crossover Patients” dataset, the PFS is defined as the time from the day of the last disease assessment, before the first administration of the combination, to the date of documented progressive disease (PD) by IMWG criteria or death (regardless of the cause of death). The same censoring rules described above for PFS calculation will be considered.

Secondary endpoints.

Objective response is defined as having minor response (MR) or better as best overall response based on the IMWG criteria (See Appendix 5 of the clinical protocol). The **objective response rate (RR)** is calculated as the number of objective responders divided by the number of patients in the “All Evaluable Patients” and “All Randomized Patients” analysis sets.

For patients within the “All Crossover Patients” dataset, the reference value for the calculation of response after crossover will be the protein value determined immediately before the administration of the combination of plitidepsin plus dexamethasone after crossover.

The **duration of objective response (DR)** will be analyzed in all patients for whom at least a MR has been observed. Duration of response will be calculated from the date of first documentation of response (not the confirmation) to the date of disease progression or death with the same censoring rules as PFS.

Overall survival (OS) is defined as the time from the date of randomization to the date of death or last contact.

Symmetry of evaluations.

Assessments must be done consistently in both treatment arms to ensure a symmetrical assessment of tumor response and progression. Every effort should be made to ensure that

these assessments are done on the required date, although a window of ± 2 days will be allowed.

Sensitivity analyses of PFS.

The impact of potential asymmetry of assessments or missing tumor evaluations on the PFS analysis will be assessed by three imputation analyses as follows:

In the key primary analysis of PFS, a patient’s event date is taken as the first date of documented disease progression based on IMWG criteria. This may potentially delay the time to actual disease progression, especially when there is a missing assessment prior to the documented disease progression.

In the first sensitivity analysis, the midpoint of the last two assessment dates on or prior to the documented disease progression will be used to impute the actual date of the disease progression. For those patients who have disease progression in the first assessment, the midpoint of randomization date and the documented disease progression will be used. For those patients who die, the midpoint between last disease assessment without PD and the date of death will be used. For patients without documented disease progression, the PFS will be censored following the same rules than in the main analysis.

In the second sensitivity analysis, the following imputation method will be used to make sure the disease assessments fall exactly ix4 weeks after randomization.

Recorded Time Window (weeks from randomization)	Imputed Time (weeks from randomization)
[0 ; 6 [4
[6 ; 10 [8
[10 ; 14[12
...	...
[i x 4 – 2 ; i x 4 + 2[i x 4

In the third sensitivity analysis, disease progression will be assumed for the first missing scheduled assessment following the last evaluation without progression.

A sensitivity analysis of PFS in the “All Evaluable Patients” population according to IRC and investigator assessment will be performed in order to present the results in the population described in the protocol.

Due to the variability of the protein used for the disease assessment, a sensitivity analysis of PFS requiring the confirmation of the disease progression by IRC assessment will be performed. Patients who die within the timeframe expected for the confirmation of PD, will be considered as PD confirmed by death. Those patients without confirmation of PD with a second disease assessment due to crossover, further antitumor therapy, lost to follow-up or other reasons, will be censored. The same censoring rules described above for PFS calculation will be considered.

6.2 Efficacy analysis methods

6.2.1 Primary endpoint

For the evaluation of the main primary endpoint (PFS), the "All Randomized Patients" population, the data from the Independent Review Committee (IRC), and the unstratified log-rank test will be used to compare both treatment arms. The final PFS analysis will be performed when at least 210 progression or death events are observed.

Cox regression will be used to calculate the risk reduction in PFS

6.2.2 Supportive PFS analyses

A stratified log-rank test for the main endpoint (PFS by IRC) will be performed as supportive analysis.

A Cox regression stratifying by randomization factors and using only treatment as covariate will be used to calculate the risk reduction in PFS.

PFS by investigator assessment in the 'All Randomized Patients' population will be analyzed according to the Kaplan-Meier method. The corresponding unstratified and stratified log-rank tests will be used to evaluate the differences between. Besides, Cox regressions will be performed to calculate the risk reduction in PFS, stratifying by randomization factors and using only treatment as covariate.

The reasons for censoring, and the concordance between the IRC and investigator evaluation of PFS will be shown using counts and percentages.

6.2.3 Secondary analyses

Overall survival:

Although the study is powered for the evaluation of the main endpoint PFS, two analyses of OS will be performed to ascertain if a trend in OS is observed in favor of the experimental arm. A first analysis of OS will be performed concomitantly with the final PFS analysis. In addition, a second analysis of OS will be performed when 80% death events (approximately 200 death events) have occurred or 24 months after the inclusion of the last patient, whichever occurs first. At the interim OS analysis the significance level determined by the O'Brien-Fleming boundary with overall 2.5% 1-sided significance level will be used.

OS analyses will be performed according to the Kaplan-Meier method and the unstratified and stratified log rank tests will be used in order to ascertain if clinically significant OS effect in favor of the experimental arm is observed.

It is anticipated that an indeterminate number of patients in the control arm will switch treatment after progression to plitidepsin plus dexamethasone. This could cause the size of the effect on OS to be difficult to interpret. Consequently, if the OS results show to be substantially influenced by crossover, the Sponsor will study the estimated effect of crossover in a first sensitivity analysis excluding the patients who crossed over and a second analysis censoring survival at the time of crossover. Estimates of the unbiased effect in survival will be studied by means of, rank preserving structural failure time (RPSFT)

models for correcting for treatment changes (2), by the inverse probability of censoring weighting (IPCW) method (6) and by means of the two-stage method proposed by Latimer *et al.* (7) in order to try to control any bias caused by treatment crossover.

The following time-dependent covariates will be included in the IPCW analysis: ECOG, Body Surface Area (BSA), m-protein value (serum/urine), number of adverse events grade \geq 3, bone marrow plasma cells, creatinine, LDH, hemoglobin and corrected serum calcium. Also, baseline covariates such as gender, age, MM type (i.e.: IgG, IgA, light chain myeloma, non-secretory), number of prior lines of anticancer treatment, status (relapsed vs. relapsed/refractory), refractory status to bortezomib, lenalidomide/thalidomide prior therapy, refractory status to last prior therapy, refractory status to IMiD therapy, refractory status to PIs therapy, genetic risk, previous SCT, time from diagnosis to randomization, time from last progression before randomization, International Staging System, Durie-Salmon stage, presence of plasmacytomas, presence of lytic lesions, number of plasmacytomas, sum of the dimensions of plasmacytomas, will be included.

The reasons for censoring of OS will be shown using counts and percentages.

An analysis will be carried out in the subpopulation of patients without crossover or subsequent therapy in order to investigate the isolated effect of study treatments in survival in this subpopulation. It will be also carried out in the subpopulation of patients without crossover or subsequent therapy and with event in the primary analysis of PFS by IRC.

Response rate:

Binomial estimates with exact 95% CIs will be calculated for the analysis of response rate. Randomized patients not evaluable for response will be excluded from the denominator exclusively for the futility analysis, but will be included in all the final efficacy analyses. A supportive analysis will be also done in the “All Evaluable Patients” population.

The magnitude of response, in patients with secretory MM, will be described by waterfall plots showing the best M-spike reduction from baseline.

A supportive analysis of response rate will be performed taking into account PR or better as best overall response based on the IMWG criteria.

Duration of response:

Duration of objective response will be analyzed according to the Kaplan-Meier method and compared between treatment groups using the log-rank test.

DR requiring confirmation of PD for determination of PFS will be analyzed according to the Kaplan-Meier method and compared between treatment groups using the log-rank test.

DR for patients who have PR or better as best overall response based on the IMWG criteria will be calculated as a supportive analysis.

Time to response:

Time to response will be analyzed according to the Kaplan-Meier method and compared between treatment groups using the log-rank test.

Time to response for patients who have PR or better as best overall response based on the IMWG criteria will be also calculated as a supportive analysis.

Analysis of crossover:

Descriptive frequency tables with the number of patients who switch from Arm B to Arm A after disease progression will be calculated.

Exploratory intrapatient comparison of response and PFS (before and after crossover) will be performed for patients who switch from Arm B to Arm A after disease progression.

The patients within the “All Crossover Patients” dataset will be listed with the cycle when the crossover occurs, and the response and PFS before and after crossover.

A comparison of the baseline characteristics in patients with Crossover *vs.* No crossover will be done to rule out that patients with crossover can have a better prognosis than patients without crossover. For two-stage method a logistic stepwise regression and the comparison of PFS between patients with crossover versus patients with no crossover is performed to check the assumption of no ‘unmeasured confounders’. Post-progression survival data is adjusted by a Weibull parametric accelerated failure time model.

A listing of patients with crossover will be provided in order to confirm if PD was seen before crossover and if this PD was confirmed.

Statistics of the time (in months) from study initiation to crossover will also be included.

Analysis of prognostic factors, subgroup analysis and multivariate analyses:

Univariate evaluation of the influence of different prognostic factors on the main efficacy endpoints will be performed by using the following covariates: Gender, age, baseline ECOG, Body Surface Area (BSA), MM type (i.e.: IgG, IgA, light chain myeloma, non-secretory), number of prior lines of anticancer treatment, status (relapsed *vs.* relapsed/refractory) refractory status to bortezomib, lenalidomide/thalidomide prior therapy, refractory status to last prior therapy, refractory status to IMiD therapy, refractory status to PIs therapy, genetic risk, previous SCT, time from diagnosis to randomization, time from last progression before randomization, International Staging System, Durie-Salmon stage, bone marrow plasma cells, bone lytic lesions (Y/N), plasmacytomas at baseline (Y/N), number of lesions at baseline, sum of the dimensions of plasmacytomas, creatinine (≥ 2 mg/dl *vs.* < 2 mg/dl), LDH, hemoglobin and corrected serum calcium (>11.5 mg/100ml *vs.* ≤ 11.5 mg/100ml).

Exploratory subgroup analyses will be performed by means of logistic regression, Kaplan-Meier analysis and Cox regression. The different subgroup analyses will be summarized by means of Forest plots.

Cox proportional hazard models for PFS and OS and logistic regression models for RR will include the prognostic factors specified for the univariate analysis. More relevant and explanatory covariates from the univariate analysis will be included in the multivariate analyses (p-value < 0.10). Prognostic factors with more than 10% missing values will be excluded in the multivariate analyses.

The analyses above mentioned will be also performed for the sensitivity analysis of PFS with confirmation of PD by IRC.

In addition, and in order to check if there are differences in the main efficacy endpoint between different continents/geographical areas, multivariate analyses of PFS by IRC, adding region as a covariate, will be performed. The variable “region” will be created with four categories (Europe, Asia, Oceania, and USA) and then three Cox regressions will be performed.

- 1) PFS by IRC with arm, region and interaction term.
- 2) PFS by IRC with arm and region as main effects.
- 3) Full model selected in the multivariate analysis of PFS by IRC, including region as variable.

Symmetry of evaluations.

Wilcoxon test will be used to compare time to disease assessments between treatment arms. Moreover, Kaplan-Meier curves of the time from randomization to first and second disease assessment will be plotted.

An analysis of the median time window between the first documentation of PD and PD confirmation in a second assessment will be done to rule out that confirmation of PD could have been advanced or delayed in any of the treatment groups.

Sensitivity analyses of PFS.

For the three sensitivity analyses using imputation methods for the date of progression, similar unstratified log-rank test as for the key primary PFS analysis will be performed, based on the imputed data sets.

Interval censoring methods will be used for the comparison of PFS in both arms by IRC and investigator assessment. An iterative algorithm developed by Turnbull(3) will be used to compute a non-parametric maximum likelihood estimate of the cumulative distribution function for the data. After that, the log-rank score of permutational test will be calculated and the normalized test statistic and associated p-value will be presented to test the difference between the two treatment groups.

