5 SAMPLE CONSIDERATIONS

5.1 Randomization

Patients fulfilling all eligibility criteria will be stratified according to the Eastern Cooperative Oncology Group (ECOG) Performance Status (PS) score (0 and 1 vs. 2) and Durie-Salmon stage at diagnosis (I/II vs. III) and then randomized using a 2:1 randomization procedure to Arm A (plitidepsin in combination with dexamethasone) or Arm B (dexamethasone alone). Randomization will be used to avoid bias in the assignment of patients to treatment, and to increase the likelihood that known and unknown patient attributes (e.g., demographics and baseline characteristics) are evenly balanced across treatment groups.

Randomization of patients should occur as close in time as possible before administration of the first dose of study drug(s) and must occur within 7 days of the patient receiving the first dose of study treatment. The randomization number and treatment code will be assigned after phoning into the Interactive Voice Response System (IVRS).

On the basis of the patient identification and stratum information, the IVRS will assign a treatment code, which will dictate the treatment assignment for that patient.

Patients will be assigned to each group by strata random list, so that a patient will have a two-thirds chance of getting Arm A (plitidepsin in combination with dexamethasone) and a one-third chance of getting Arm B (dexamethasone alone). The random permuted blocks method will be used; the size of the blocks in the randomization list will be fixed and not accessible to investigators. To select the blocks, a uniform (0, 1) variable with a random seed will be used.

5.2 *Sample size*

The number of patients randomized in the trial has been calculated based on PFS estimates obtained from the previous phase II study (APL-B-014-03).

1. **Arm A** (plitidepsin plus dexamethasone combination): approximately 167 patients.
2. **Arm B** (dexamethasone single agent): approximately 83 patients.

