Approximately 210 progression or death events would be needed in this trial to detect a HR of 0.625 in favor of the combination arm (equivalent to an increase of 60% in PFS, i.e., from 10 to 16 weeks, 12 to 19.2 weeks, 16 to 25.6 weeks) with 90% power and 1-sided 2.5% significance level. As a preliminary hypothesis, it is estimated that up to 250 randomized patients will be needed to achieve the 210 events in 24-30 months. For the calculation of the number of events needed, the target HR to be detected is 0.625, with 90% power and 2.5% unilateral significance level. This is equivalent to a minimum 60% increase in PFS, which has been considered statistically and clinically significant by the Sponsor.

An early futility analysis will be performed with the data collected when 40 patients in Arm A are evaluable for response. A response rate (IMWG criteria) of at least 30% (twelve or more responses by IRC review) will be taken as threshold for continuation of the study. A minimum response rate of 30% has been considered as clinically significant in this setting. This result will ensure that the lower limit of the exact binomial 95% Confidence Interval for the response rate will be greater than 15% (95% CI in case of 12 responses would be 16.6% - 46.5%).

However, the efficacy and safety information from all randomized patients in both arms at that time will be used by the independent data monitoring committee (IDMC) to provide the Sponsor with a recommendation for further study conduct.

The final PFS analysis will be performed when at least 210 progression or death events are observed.

An interim analysis of OS will be performed concomitantly with the final PFS analysis. In addition, a final analysis of OS will be performed when 80% of death events (approximately 200 death events) have occurred or 24 months after the inclusion of the last patient, whichever occurs first. At the interim OS analyses, the significance level determined by the O'Brien-Fleming (1) boundary with overall 2.5% 1-sided significance level will be used.

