11.3.4 Secondary analyses

11.3.4.1 OS analyses

Table 11.3.4.1.1 OS (“All Randomized Patients” population)

	Arm A	Arm B	Parameter	p-value
N				
Events				
Censored				
Median OS			Log-Rank: HR (95% CI) :	LR: HR:
OS at 12 months			Diff:	
OS at 24 months			Diff:	

Kaplan-Meier plot will be also shown (Figure 11.3.4.1.1).

Table 11.3.4.1.2 OS stratified comparison (“All Randomized Patients” population)

	Arm A	Arm B
Stratum 1		
N		
Events		
Censored		
Median OS		
OS at 12 months		
OS at 24 months		
Stratum 2		
N		
Events		
....		
....		
Log-Rank* / p-value** / HR (95% CI) :		

(*)Stratified log-rank test statistic. (**) p-value from stratified log-rank test

Table 11.3.4.1.3 OS (“All Randomized Patients” population excluding crossover patients)

	Arm A	Arm B	Parameter	p-value
N				
Events				
Censored				
Median OS			Log-Rank: HR (95% CI) :	LR: HR:
OS at 12 months			Diff:	
OS at 24 months			Diff:	

Kaplan-Meier plot will be also shown (Figure 11.3.4.1.3).

Table 11.3.4.1.4 OS (“All Randomized Patients” population censoring crossover patients at cross-over date)

	Arm A	Arm B	Parameter	p-value
N				
Events				
Censored				
Median OS			Log-Rank: HR (95% CI) :	LR: HR:
OS at 12 months			Diff:	
OS at 24 months			Diff:	

Kaplan-Meier plot will be also shown (Figure 11.3.4.1.4).

Table 11.3.4.1.5 OS (“All Randomized Patients” population and IPCW method)

	Arm A	Arm B	Parameter	p-value
N				
Events				
Censored				
Median OS			Log-Rank: HR (95% CI) :	LR: HR:
OS at 12 months			Diff:	
OS at 24 months			Diff:	

Kaplan-Meier plot will be also shown (Figure 11.3.4.1.5).

Table 11.3.4.1.6 OS (“All Randomized Patients” population and RPSFT method)

	Arm A	Arm B	Parameter	p-value
N				
Events				
Censored				
Median OS			Log-Rank: HR (95% CI) :	LR: HR:
OS at 12 months			Diff:	
OS at 24 months			Diff:	

Kaplan-Meier plot will be also shown (Figure 11.3.4.1.6).

A forest plot (Figure 11.3.4.1.7) with the summary of hazard ratios for PFS and OS in the different analysis populations will be shown to check the consistency across the different measurements.

Table 11.3.4.1.8 OS – Reason of censoring (“All Randomized Patients” population)

Reason of censoring	Arm A		Arm B	
	N	%	N	%
Alive				
Lost to follow-up				
Withdrawal of consent				

Table 11.3.4.1.9 OS (Subpopulation without crossover or subsequent therapy)

	Arm A	Arm B	Parameter	p-value
N				
Events				
Censored				
Median OS			Log-Rank: HR (95% CI) :	LR: HR:
OS at 12 months			Diff:	
OS at 24 months			Diff:	

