Kaplan-Meier plot will be also shown (Figure 11.3.4.1.9).

Table 11.3.4.1.10 OS (Subpopulation of patients with event in the primary analysis and without crossover or subsequent therapy)

	Arm A	Arm B	Parameter	p-value
N				
Events				
Censored				
Median OS			Log-Rank: HR (95% CI) :	LR: HR:
OS at 12 months			Diff:	
OS at 24 months			Diff:	

Kaplan-Meier plot will be also shown (Figure 11.3.4.1.10).

Table 11.3.4.1.11 OS (“All Randomized Patients” population and Two-stage method)

	Arm A	Arm B	Parameter	p-value
N				
Events				
Censored				
Median OS			Log-Rank: HR (95% CI) :	LR: HR:
OS at 12 months			Diff:	
OS at 24 months			Diff:	

Kaplan-Meier plot will be also shown (Figure 11.3.4.1.11).

A forest plot (Figure 11.3.4.1.12) with the summary of hazard ratios for OS in the different analysis populations will be shown to check the consistency across the different measurements.

Supportive analyses needed to adjust OS by crossover by the two-stage method

Table 11.3.4.1.13 Logistic regression (Crossover patients vs no crossover patients)

Analysis of Maximum Likelihood Estimates*								
Variable Label	Variable values	DF	Parameter Estimate	Standard Error	Chi-Square	Pr > ChiSq	Odds Ratio	95% Odds Ratio Confidence Limits

* Logistic regression

See list of covariates in section 6.2.3

Table 11.3.4.1.14 PFS (Crossover patients vs no crossover patients)

	Crossover	No crossover	Parameter	p-value
N				
Events				
Censored				
Median PFS			Log-Rank: HR (95% CI) :	LR: HR:

Kaplan-Meier plot will be also shown (Figure 11.3.4.1.14).

Table 11.3.4.1.15 Post progression survival (Weibull adjustment)

Analysis of Maximum Likelihood Parameter Estimates							
Parameter		DF	Estimate	Standard Error	95% Confidence Limits	Chi-Square	Pr > ChiSq
Intercept							
Treatment arm	-						
Treatment arm	Crossover						
Scale							
Weibull Shape							

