
15 Revision History

From Statistical Analysis Plan v5.0 to v6.0:

This amendment of the Statistical Analysis Plan (SAP) is intended to incorporate an additional overall survival sensitivity analysis in order to better characterize the impact of crossover in arm B. The addition of this new analysis was consulted and agreed with the EMA Product Team Members in a clarification meeting that took place on 12th of June of 2017.

The nature of these analyses is supportive for the secondary analyses of overall survival already described in previous versions of the SAP.

Rational of changes:

In order to improve the characterisation of the actual impact of crossover in those patients who switched from DXM (Arm B) to plitidepsin plus DXM (Arm A), an analysis based on the two-stage method proposed by Latimer *et al.* (7) is performed.

Briefly, the two-stage estimation is a method that provides a good fit to the treatment change mechanics often observed in oncology. Usually, switching is only permitted after disease progression, but this is likely to occur shortly afterwards. In that case, disease progression can be used as a secondary baseline for patients in the control group. Fitting a Weibull model would be expected to produce a reasonable estimate of the effect resulting from switching to the experimental treatment, provided that 1) the model fits the data, 2) “no unmeasured confounders” are present at the secondary baseline, and 3) switching occurs soon after the secondary baseline. The resulting acceleration factor associated with treatment change could then be used to “shrink” survival times in switching patients to derive a counterfactual survival dataset upon which standard survival analysis could be undertaken.

CHANGES:

Included changes are highlighted in *Italic Bold*.

PAGE 16-17: Section 6.2.3 Secondary analyses – Overall survival

Original text:

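### The two-stage and RPSFT survival tables ask for an ordinary log-rank p-value and 95% CI on adjusted times, with no allowance for the estimated adjustment factor, so the error bars would be too narrow

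*SAP*

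**What the plan says.** Section 6.2.3 of the SAP plans OS analyses by Kaplan-Meier and log-rank tests. If crossover proves to have materially affected OS, adjusted estimates follow: "Estimates of the unbiased effect in survival will be studied by means of, rank preserving structural failure time (RPSFT", then IPCW, then the two-stage method. The section does not say how their standard errors, confidence intervals or p-values are obtained.

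- **Two-stage.** The v6.0 rationale in section 15 explains that the acceleration factor shrinks switchers' survival times to "derive a counterfactual survival dataset upon which standard survival analysis could be undertaken". Table 11.3.4.1.11 then reports log-rank, HR with 95% CI, and a p-value for each. Under the line "Supportive analyses needed to adjust OS by crossover by the two-stage method", Table 11.3.4.1.15 prints a standard error for the Weibull crossover term, but nothing carries that uncertainty into Table 11.3.4.1.11.
- **RPSFT.** Table 11.3.4.1.6 ("population and RPSFT method") has the same cells as the unadjusted OS table. Section 9 adds only that Stata will be used.
- **Default.** Section 11.3.2 falls back on the unstratified test for time-to-event variables where none is named.

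Neither document mentions a bootstrap, a test-based CI or carrying the ITT p-value over to the adjusted analysis. The adjusted HRs also feed the OS forest plots (Figures 11.3.4.1.7 and 11.3.4.1.12).

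**The concern.** Both methods replace observed survival times by times that depend on an estimated factor. Two-stage estimates it from post-progression survival in Arm B. RPSFT chooses the value that balances counterfactual survival between the randomized arms. A log-rank test or Cox model run on the resulting dataset takes the factor as known, so it understates the variance.

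RPSFT raises a further point. Its factor is derived from the randomized comparison itself, so it contains no more evidence against the null than the ITT test. A smaller p-value in Table 11.3.4.1.6 than in the ITT table would be an artefact.

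What is at stake is how the crossover-adjusted OS results are read. The forest plots set adjusted and unadjusted HRs side by side to show consistency. The two-stage analysis was added after discussion with a regulator, so it will be looked at. Intervals that are too short invite the conclusion that an OS benefit appears once crossover is removed.

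**Working it through.** **Plan's own figures.** The documents state no error rate for the adjusted analyses, so the design figures were reproduced to confirm the inputs. The SAP says "Approximately 210 progression or death events would be needed in this trial to detect a HR of 0.625 in favor of the combination arm" "with 90% power and 1-sided 2.5% significance level", and that "a patient will have a two-thirds chance of getting Arm A (plitidepsin in combination with dexamethasone". Schoenfeld: (1.960 + 1.282)² / [(1/3)(2/3)(ln 0.625)²] = 10.51 / (0.2222 × 0.2209) ≈ 214, or 215 rounded up. That is within 3% of 210, and 210 events give 89.4% power. Deaths at the OS analysis in the protocol note: 195/255 = 76.5%.

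**Error level.** For OS, "At the interim OS analysis the significance level determined by the O'Brien-Fleming boundary with overall 2.5% 1-sided significance level will be used". This corresponds to 5% two-sided, the level that the shells' 95% CIs imply.

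**Inputs from the documents.** 2:1 allocation (simulated as 170 vs 85); 60 months' accrual plus 24 months' follow-up; crossover only for progression at 8 weeks or later; control median PFS 10 to 16 weeks (2.3 to 3.7 months).

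**Assumptions.**
- Exponential PFS and OS with no effect of either drug.
- OS median 12, 17 or 24 months. The 17 is the phase II figure in the protocol; 24 gives about 76% deaths.
- Uptake of 30%, 60% or 90% among eligible patients, so that 14–16%, 28–32% or 42–48% of Arm B cross over.
- Switching unrelated to prognosis.

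Each scenario had 1,500 runs. RPSFT used log-rank g-estimation with re-censoring. Two-stage used a Weibull accelerated failure time model without covariates. Both were followed by an ordinary log-rank test on the adjusted times.

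**Two-sided error at nominal 5%:**

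| Arm B crossing over | Two-stage | RPSFT, on-treatment time counted | RPSFT, all post-switch time counted |
|---|---|---|---|
| about 15% | 6–7% | 7–8% | 8–10% |
| about 30% | 7–10% | 10–13% | 14–18% |
| about 45% | 10–13% | 17% | 24–28% |

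The unadjusted ITT test stayed at 4–6%. Monte Carlo error is about 0.6 to 1 point. In the on-treatment RPSFT runs, 0.3–4% had no solution and were dropped.

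**Why the intervals are short.** At OS median 24 months and 32% crossover, with all post-switch time counted, the standard error reported by the naive analysis against the true SD of the log HR was:
- two-stage 0.153 vs 0.177. Ratio 0.864; 1.96 × 0.864 = 1.69; implied error 2[1 − Φ(1.69)] ≈ 9%.
- RPSFT 0.155 vs 0.223. Ratio 0.695; 1.96 × 0.695 = 1.36; implied error ≈ 17%.

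The simulated values for the same scenario were 9.2% and 16.1%.

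**Closed-form check for RPSFT.** If f is the share of Arm B time after the switch and all of it counts as treated, the adjusted log HR is roughly the ITT log HR divided by (1 − f), while the naive standard error hardly changes. Error is then about 2[1 − Φ(1.96(1 − f))]: 7.8% at f = 0.10, 14.2% at 0.25 and 24.0% at 0.40. This follows the last column.

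**Does the remedy work?** RPSFT with the ITT p-value has the ITT error by construction, 4–6%. For two-stage, a bootstrap of the whole procedure (400 trials, 100 resamples each) gave 5.8%, 4.3% and 4.3%, against 8.5%, 8.5% and 11.3% for the naive test in the same trials.

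**The case against.** A table shell shows what is reported, not how it is calculated, and the same cells appear in nearly every time-to-event table in the SAP. The remark about standard survival analysis sits in the revision history, describes the two-stage method in general and is conditionally worded. For RPSFT there is only a software name and a cited paper. A competent programmer might well use a bootstrap or a test-based interval.

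Much of this stands for RPSFT: that its table would be computed naively is an inference from the shell and the section 11.3.2 default. It is weaker for two-stage, where the only description of the analysis step in the SAP points to the ordinary one. In neither case does the SAP require anything better.

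The second objection is that these analyses are supportive, conditional on crossover mattering, have no decision rule, and sit beside unadjusted OS results in Tables 11.3.4.1.1 and 11.3.4.1.2. This is correct and limits the consequence. A reader might infer that the trial's type I error is inflated. The documents do not support that: the primary analysis is PFS, and no alpha rests on the adjusted OS estimates.

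The third is that the size rests on a crossover rate that the SAP declines to predict. This also stands. No single inflation figure can be derived from the documents, and one range should not be quoted for both methods.

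**Conclusion.** The point holds. As written, the two-stage error bars are too narrow. For RPSFT the SAP is silent on variance, and following its shell and default test leads to the same fault, usually in larger measure.

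Under no effect, two-stage error is about 6–13% and RPSFT about 7–28% across assumed crossover of 14–48% of Arm B. Inflation appeared in every scenario run. The figures rest on exponential times, unconfounded switching and no covariates. For RPSFT they also depend on whether on-treatment or all post-switch time counts as treated, which the SAP does not say.

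Two wider readings should be resisted. A reader might extend the criticism to the IPCW table. IPCW does not shrink survival times, was not simulated here, and the SAP's own IPCW reference is by title about IPCW log-rank tests, so no change is proposed there. A reader might also blame the lack of re-censoring. That is mainly a matter of bias, and the RPSFT runs applied it and still showed the inflation.

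**What to change.** State in section 6.2.3 how each interval and p-value is obtained:

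- **RPSFT (Table 11.3.4.1.6):** report the ITT log-rank p-value, with a test-based CI consistent with it or a bootstrap CI. State whether on-treatment or all post-switch time counts as treated.
- **Two-stage (Table 11.3.4.1.11):** resample patients within arm, repeat every step (Weibull fit, shrinkage of switchers' times, Cox model), and take the CI and p-value from the bootstrap.
- **Presentation:** replace the naive log-rank and HR p-values and CIs in both tables, and use the new intervals in Figures 11.3.4.1.7 and 11.3.4.1.12. Leave the IPCW table as it is.

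No new data are needed. The cost is a few lines of SAP text, a bootstrap loop and wider intervals.
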